12.4 ECOG Performance Status

Grade	Description
0	Normal activity. Fully active, able to carry on all pre-disease performance without restriction.
1	Symptoms, but ambulatory. Restricted in physically strenuous activity, but ambulatory and able to carry out work of a light or sedentary nature (e.g., light housework, office work).
2	In bed <50% of the time. Ambulatory and capable of all self-care, but unable to carry out any work activities. Up and about more than 50% of waking hours.
3	In bed >50% of the time. Capable of only limited self-care, confined to bed or chair more than 50% of waking hours.
4	100% bedridden. Completely disabled. Cannot carry on any self-care. Totally confined to bed or chair.
5	Dead.
* As published in Am. J. Clin. Oncol.: Oken, M.M., Creech, R.H., Tormey, D.C., Horton, J., Davis, T.E., McFadden, E.T., Carbone, P.P.: Toxicity And Response Criteria Of The Eastern Cooperative Oncology Group. Am J Clin Oncol 5:649-655, 1982. The Eastern Cooperative Oncology Group, Robert Comis M.D., Group Chair.	

12.5 Recommended Supportive Care Guidelines for Tumor Lysis Syndrome Prevention and Treatment in Subjects with CLL and DLBCL

1. Subjects with CLL and DLBCL will be admitted to the inpatient service the day prior to dinaciclib treatment for a minimum of the first treatment (C1D1 dose).
2. Premedication and IV hydration for dinaciclib for CLL and DLBCL are described in Section 5.2.1.3.1 (Table 6).
3. Using the Cairo-Bishop definition of laboratory TLS, K, calcium, potassium, and uric acid will be evaluated at 3 and 5 hours after the start of the first dinaciclib infusion (C1D1) as part of a TLS work-up (Section 5.2.1.3.3). Subjects with a positive TLS work-up should remain in the hospital and follow-up should be initiated. If necessary, subjects must be admitted overnight for observation.
 - If serum potassium > 4.5 mmol/L, then the subject should receive a 30 g dose of Kayexalate (or equivalent).
 - If serum potassium > 5.0 mmol/L, then the subject should receive 10 units of IV regular insulin and one ampule of D50 IV. During this time period, trial treatment administration should be discontinued.
 - If serum potassium > 5.5 mmol/L, then the subject should be considered for emergent intermittent or continuous hemodialysis.

During this time period, trial treatment administration should be discontinued.

Subjects who do not have laboratory TLS may receive Dose 2 (Day 8) of Cycle 1, as well as all subsequent therapies, as an outpatient.

This will allow inpatient monitoring of subjects during the most critical window of vulnerability to tumor lysis, yet allow subjects who tolerate dinaciclib to eventually be treated in the outpatient setting.

4. Subjects who develop clinical evidence of CRS or who have hyperkalemia requiring dialysis will receive immediate steroid therapy with 20 mg of IV dexamethasone (or equivalent). CRS is described in the NCI CTCAE current version. It occurs during or shortly after drug infusion and generally resolves within 24 hours of completing the infusion. Generally, the first manifestation of this syndrome is tachycardia followed by a constellation of symptoms. Subjects starting therapy with a normal pulse whose rate increases to >100 beats per minute post-therapy should be administered therapy for CRS. The signs and symptoms of CRS may include allergic reaction (including drug fever), arthralgia, bronchospasm, cough, dizziness, dyspnea, fatigue, headache, hypertension or hypotension, myalgia, nausea, pruritus, rash, rigors, chills, sweating, tachycardia, tumor pain, urticaria, and vomiting.
5. Subjects who require dialysis for hyperkalemia and/or other symptoms of TLS will be administered prophylactic antibiotics for gram-negative organisms (Zosyn 4.5 g IV every 8 hours or equivalent) and gram-positive organisms (vancomycin 1 g IV every 12 hours or equivalent) until dialysis is discontinued.

6. Subjects requiring intervention for TLS or demonstrating CRS symptoms should have their serum electrolytes, phosphate, calcium and magnesium checked every 8 to 12 hours post-therapy. If treatment is required, Amphojel or equivalent phosphate-binding agents are recommended. In this setting, calcium supplementation should only be given for symptomatic hypocalcemia to avoid renal precipitation of calcium phosphate crystals.
7. Subject may be discharged home the morning following the first dinaciclib infusion once their chemistry laboratory results have been reviewed by the treating physician.
8. It is recommended to inform the local renal consultant service of inpatient admissions for the first dinaciclib treatment for each subject. Administration of the first dinaciclib dose should occur at the beginning of the day.

12.6 Drugs that Interact with CYP3A4

Information for drug interactions with cytochrome P450 isoenzymes can be found at <http://medicine.iupui.edu/flockhart/>.

12.7 Revised iwCLL Response Guidelines

CLL response assessment is based on the 2008 International Workshop (iwCLL) guidelines (Blood 2008;111:5446-5456) with the following clarifications/revisions.

NCI-WG CLL Response Criteria^A	
Complete Remission (CR)	
Requires ALL of the following criteria as assessed at least 2 months after completion of therapy:	
Peripheral blood lymphocytes (x10 ⁹ /L)	<4
Lymphadenopathy	None by physical exam and CT scan
Hepatomegaly or splenomegaly	None by physical exam and CT scan
Symptoms	None
Blood counts:	
Neutrophils (x10 ⁹ /L), and	>1.5 without need for exogenous growth factors
Platelets (x10 ⁹ /L), and	>100 without need for exogenous growth factors
Hemoglobin (g/dL)	>11 without red blood cell transfusion or need for exogenous erythropoietin
Bone marrow	For subjects in clinical trials, at least 2 months after the last treatment and if clinical and laboratory criteria for CR has been achieved: normal cellularity for age; <30% of nucleated cells are lymphocytes; no lymphoid nodules. If hypocellular, repeat bone marrow biopsy at 4 weeks, or until peripheral blood counts have recovered (time interval should not exceed 6 months after last treatment).
CR with Incomplete Marrow Recovery (CRi)	
Meets all criteria for CR but have persistent anemia or thrombocytopenia or neutropenia related to drug toxicity	
Nodular Partial Remission	
Meets all criteria for CR but lymphoid nodules are present in the bone marrow sample obtained at least 2 months after last treatment.	
Partial Remission (PR)	
The following criteria must be documented for a minimum of 2 months:	

Blood lymphocytes, and
 
Lymphadenopathy, and
	
≥50% decrease from baseline
 
≥50% decrease in the sum products of up to 6 lymph nodes or in the largest diameter of the enlarged lymph node(s) from baseline.
 
and
 
No increase in any lymph node, and no new enlarged lymph node (in lymph nodes <2 cm, an increase of < 25% is not considered significant)


Liver or spleen (if abnormal before therapy)
 
Plus, one or more of the following:
 
Neutrophils
 
Platelets
 
Hemoglobin
	
≥50% decrease from baseline (CT scan [clinical trials] or palpitation [general practice])
 
>1.5 x10⁹/L (1500/μL) without need for exogenous growth factors
 
>100 x10⁹/L (100,000/μL), or 50% improvement over baseline, without need for exogenous growth factors
 
>11 g/dL (110 g/L), or 50% improvement over baseline, without red blood cell transfusion or need for exogenous erythropoietin

Progressive Disease (PD)
 
Characterized by at least one of the following during or after therapy:
	

Lymphadenopathy	New lesion, such as enlarged lymph nodes (>1.5 cm), splenomegaly, hepatomegaly, or other organ infiltrates or $\geq 50\%$ increase in greatest determined diameter of any previous site
Liver or spleen	$\geq 50\%$ increase from previous noted enlargement or the de novo appearance of hepatomegaly or splenomegaly
Blood lymphocytes	$\geq 50\%$ increase with ≥ 5000 B lymphocytes per microliter
Cytopenia	Progression of cytopenia attributable to CLL which occurs at least 3 months after treatment as documented by: 
 - decrease of Hb levels by >20 g/L or to >100 g/L - decrease of platelets by $>50\%$ or to $<100 \times 10^9$/L if the marrow biopsy demonstrates an infiltrate of clonal CLL cells
Other	Transformation to a more aggressive histology (e.g., Richter syndrome)
Stable disease (SD)	
Subjects who have not achieved a CR or a PR, and who have not exhibited PD	
A Blood. 2008;111:5446-5456.	

12.8 International Myeloma Working Group criteria for response assessment in multiple myeloma (IMWG criteria)

Durie et al. International uniform response criteria for multiple myeloma. *Leukemia*. 2006; 20:1467-1473.

Table 5 International Myeloma Working Group uniform response criteria: CR and other response categories

Response subcategory	Response criteria^a
sCR	CR as defined below plus Normal FLC ratio and Absence of clonal cells in bone marrow ^b by immunohistochemistry or immunofluorescence ^c
CR	Negative immunofixation on the serum and urine and Disappearance of any soft tissue plasmacytomas and ≤ 5% plasma cells in bone marrow ^b
VGPR	Serum and urine M-protein detectable by immunofixation but not on electrophoresis or 90% or greater reduction in serum M-protein plus urine M-protein level < 100 mg per 24 h
PR	≥ 50% reduction of serum M-protein and reduction in 24-h urinary M-protein by ≥ 90% or to < 200 mg per 24 h If the serum and urine M-protein are unmeasurable, ^d a ≥ 50% decrease in the difference between involved and uninvolved FLC levels is required in place of the M-protein criteria If serum and urine M-protein are unmeasurable, and serum free light assay is also unmeasurable, ≥ 50% reduction in plasma cells is required in place of M-protein, provided baseline bone marrow plasma cell percentage was ≥ 30% In addition to the above listed criteria, if present at baseline, a ≥ 50% reduction in the size of soft tissue plasmacytomas is also required
SD (not recommended for use as an indicator of response; stability of disease is best described by providing the time to progression estimates)	Not meeting criteria for CR, VGPR, PR or progressive disease

Abbreviations: CR, complete response; FLC, free light chain; PR, partial response; SD, stable disease; sCR, stringent complete response; VGPR, very good partial response.

^aAll response categories require two consecutive assessments made at anytime before the institution of any new therapy; all categories also require no known evidence of progressive or new bone lesions if radiographic studies were performed. Radiographic studies are not required to satisfy these response requirements.

^bConfirmation with repeat bone marrow biopsy not needed.

^cPresence/absence of clonal cells is based upon the *k/λ* ratio. An abnormal *k/λ* ratio by immunohistochemistry and/or immunofluorescence requires a minimum of 100 plasma cells for analysis. An abnormal ratio reflecting presence of an abnormal clone is *k/λ* of > 4:1 or < 1:2.

^dRefer to Table 4 for definitions of measurable disease.

Table 6. International Myeloma Working Group uniform response criteria: disease progression and relapse

Relapse subcategory	Relapse criteria
Progressive disease ^a To be used for calculation of time to progression and progression-free survival end points for all patients including those in CR (includes primary progressive disease and disease progression on or off therapy)	Laboratory or Biochemical Relapse or Progressive Disease: requires any one or more of the following: Increase of $\geq 25\%$ from baseline in Serum M-component and/or (the absolute increase must be ≥ 0.5 g/dl) ^b Urine M-component and/or (the absolute increase must be ≥ 200 mg/24 h Only in patients without measurable serum and urine M-protein levels: the difference between involved and uninvolved FLC levels. The absolute increase must be >10 mg/dl. Bone marrow plasma cell percentage: the absolute % must be $\geq 10\%$ ^c Definite development of new bone lesions or soft tissue plasmacytomas or definite increase in the size of existing bone lesions or soft tissue plasmacytomas Development of hypercalcemia (corrected serum calcium > 11.5 mg/dl or 2.65 mmol/l) that can be attributed solely to the plasma cell proliferative disorder
Clinical relapse (i.e., progressive disease requiring re-treatment or alternate treatment) ^b	Clinical relapse or progressive disease requires one or more of: Direct indicators of increasing disease and/or end organ dysfunction (CRAB features) ^b It is not used in calculation of time to progression or progression-free survival but is listed here as something that can be reported optionally or for use in clinical practice 1. Development of new soft tissue plasmacytomas or bone lesions 2. Definite increase in the size of existing plasmacytomas or bone lesions. A definite increase is defined as a 50% (and at least 1 cm) increase as measured serially by the sum of the products of the cross-diameters of the measurable lesion 3. Hypercalcemia (>11.5 mg/dl) [2.65 mmol/l] 4. Decrease in hemoglobin of ≥ 2 g/dl [1.25 mmol/l] (see Table 3 for further details) 5. Rise in serum creatinine by 2 mg/dl or more [177 μ mol/l or more]
Relapse from CR ^a (To be used only if the end point studied is DFS) ^d	Any one or more of the following: Reappearance of serum or urine M-protein by immunofixation or electrophoresis Development of $\geq 5\%$ plasma cells in the bone marrow ^c Appearance of any other sign of progression (i.e., new plasmacytoma, lytic bone lesion, or hypercalcemia see below)

Abbreviations: CR, complete response; DFS, disease-free survival.

^a All relapse categories require two consecutive assessments made at anytime before classification as relapse or disease progression and/or the institution of any new therapy.

^b For progressive disease, serum M-component increases of ≥ 1 gm/dl are sufficient to define relapse if starting M-component is ≥ 5 g/dl.

^c Relapse from CR has the 5% cutoff versus 10% for other categories of relapse.

^d For purposes of calculating time to progression and progression-free survival, CR patients should also be evaluated using criteria listed above for progressive disease.

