In the Signal Detection phase, approximately 30 subjects each with rrCLL, rrMM, or rrDLBCL will be enrolled in separate cohorts. The Dose Evaluation and Signal Detection phases will further evaluate safety and characterize preliminary efficacy.

In the Signal Detection phase, an interim analysis for safety and an efficacy interim analysis for futility will be conducted for each cohort after 12 subjects have been enrolled and the last subject has completed the first response assessment (ie, after Cycle 3 for CLL and rrDLBCL, and after Cycle 2 for rrMM), or otherwise discontinued trial treatment. Enrollment will be paused during the interim analysis (Section 8.7). The results will be reviewed by the trial

[figure not shown]
team. Enrollment may resume in that cohort if the results of the safety and efficacy analysis justify continuing.

Subjects will continue on treatment until disease progression (PD) (Section 7.1.2.7 and Section 7.1.2.8), unacceptable adverse event (AE), or treatment has been completed (ie, 35 cycles [approximately 2 years]). Subjects who discontinue treatment before PD, including subjects who discontinue treatment for bone marrow transplantation or to receive any other treatment, will be followed every 12 weeks for at least 12 months until PD is documented or until the end of the trial.

The primary objective of the trial is to evaluate the safety and tolerability of the combination of pembrolizumab and dinaciclib in subjects with hematologic malignancies. Secondary objectives by tumor type include the ORR, duration of response (DOR), progression-free survival (PFS), and overall survival (OS).

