Measured or calculated ^b creatinine clearance (GFR can also be used in place of creatinine or creatinine clearance)	\geq 60.0 mL/min for subject with creatinine levels > 1.5 X institutional ULN
Hepatic	
Total bilirubin	\leq 1.5 X ULN OR
	Direct bilirubin \leq ULN for subjects with total bilirubin levels > 1.5 ULN
AST and ALT	\leq 2.5 X ULN OR \leq 5 X ULN for subjects with liver metastases
Coagulation	
INR or PT aPTT	\leq 1.5 X ULN unless subject is receiving anticoagulant therapy as long as PT or PTT is within therapeutic range of intended use of anticoagulants
Abbreviations: ALT (SGPT) = alanine aminotransferase (serum glutamic pyruvic transaminase); ANC = absolute neutrophil count; aPTT = activated partial thromboplastin time; AST (SGOT) = aspartate aminotransferase (serum glutamic oxaloacetic transaminase); CLL = chronic lymphocytic leukemia; GFR=glomerular filtration rate; INR = international normalized ratio; PT = prothrombin time; PTT = partial thromboplastin time; ULN=upper limit of normal. ^a Criteria must be met without erythropoietin dependency and without packed red blood cell (pRBC) transfusion within last 2 weeks. ^b Creatinine clearance should be calculated per institutional standard. Note: This table includes eligibility-defining laboratory value requirements for treatment; laboratory value requirements should be adapted according to local regulations and guidelines for the administration of specific chemotherapies.	

CLL –Note: The rrCLL cohort was closed to enrollment on 30-APR-2019 due to lack of accrual, and all subjects with rrCLL have discontinued from treatment. Remaining subjects with rrCLL are in survival follow-up.

10. Confirmed diagnosis of CLL as defined by 2008 iwCLL criteria.

11. Subjects must have received at least one prior therapy.

12. Must meet one or more of the following consensus criteria for initiating treatment:

- Progressive disease or marked splenomegaly and/or lymphadenopathy,
- Anemia (hemoglobin < 11 g/dL) or thrombocytopenia (platelets < 100,000/mm³),
- Unexplained weight loss \geq 10% of body weight over preceding 6 months
- National Cancer Institute CTCAE Grade 2 or 3 fatigue,

- Fevers >100°F/38°C or night sweats for greater than 2 weeks without evidence of infection,
- Progressive lymphocytosis, with an increase > 50% over a 2-month period or a doubling time < 6 months.

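### CLL partial remission needs a 50% fall in lymphocytes and in nodes even when these were normal at entry, so some responders can be scored as stable disease

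*Combined protocol and SAP*

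**What the plan says.** Section 12.7 sets the CLL response categories.

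- **PR.** The lines are joined by a conjunction, starting with "Blood lymphocytes, and", which needs a fall of at least 50% from baseline. The node line needs at least a 50% "decrease in the sum products of up to 6 lymph nodes or in the largest diameter of the enlarged lymph node(s) from baseline", with no node growing and no new enlarged node. The third line reads "Liver or spleen (if abnormal before therapy") and also asks for a 50% fall. At least one blood-count criterion must be met as well. On duration: "The following criteria must be documented for a minimum of 2 months". PR is not tied to the end of treatment.
- **CR.** "Requires ALL of the following criteria as assessed at least 2 months after completion of therapy". Lymphocytes must be below 4 x10^9/L, there must be no lymphadenopathy, and the marrow is examined at least 2 months after the last treatment. CR with incomplete marrow recovery and nodular PR both require the CR criteria.
- **SD.** The default: "Subjects who have not achieved a CR or a PR, and who have not exhibited PD".

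On entry, Section 5.1.2 (inclusion 12) says of CLL subjects: "Must meet one or more of the following consensus criteria for initiating treatment". Anemia or thrombocytopenia alone is enough. No node size or lymphocyte count is set, whereas the MM and DLBCL criteria require measurable disease. Under Section 2.1, treatment runs to progression, unacceptable toxicity, or until "treatment has been completed (ie, 35 cycles [approximately 2 years"]). Section 8.4.1 counts CR and PR in the CLL ORR.

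**The concern.** A parameter that is normal at entry has little or no room to halve. Section 12.7 recognises this for liver and spleen but is silent for lymphocytes and nodes. Having the exception on one line and not on the other two invites the reading that those two are unconditional. The MM criteria in Section 12.8 do deal with the problem, through fallbacks for unmeasurable M-protein and a presence-at-baseline condition for plasmacytomas.

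CR cannot make up for this during treatment, because it is assessed only after therapy has ended. An affected responder therefore falls to SD by default, counts as a non-responder in the CLL ORR and in the 12-subject interim count, and drops out of the duration-of-response analysis, which covers responders only (Table 19). Response is read locally (Section 7.1.2.7), so sites may also resolve the gap differently.

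**Working it through.** **1. Lymphocyte line: PR against CR.** For an entry count B (x10^9/L), PR needs a count of at most B/2; CR needs a count below 4. PR is the stricter of the two when B/2 < 4, that is, when B < 8.

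| Entry count | PR needs | CR needs |
|---|---|---|
| 80 | 40 or less | below 4 |
| 6 | 3.0 or less | below 4 |
| 3.0 | 1.5 or less | below 4 |

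So for entry counts below 8, the lesser response category sets the harder lymphocyte test. This follows from Section 12.7 alone.

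**2. Who is affected.**

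| At entry | On treatment | After treatment |
|---|---|---|
| Enlarged nodes, lymphocytes well above 8 | PR can be scored | CR possible; waiting for CR leaves ORR unchanged |
| No enlarged nodes, lymphocytes 80, hemoglobin 9 g/dL | SD if the node row is unconditional; PR possible if it is read as not applicable | CR possible if treatment stops without progression |
| Enlarged nodes that clear, lymphocytes steady at 3.0 | SD | CR possible if treatment stops without progression |
| Enlarged nodes that shrink by half or more but stay enlarged, lymphocytes steady at 3.0 | SD | Neither PR nor CR, since CR needs no lymphadenopathy |

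The after-treatment route exists because Section 7.1.5.4 has subjects who stop without confirmed progression assessed every 12 weeks.

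**3. The plan's own interim figure.** Section 8.7 says that 2 or fewer responses in 12 rule out an ORR of 39% with one-sided 90% confidence. The exact upper bound for 2/12 is the 0.90 quantile of Beta(3, 10) = 38.6%, which agrees. At a true ORR of 39%, P(X <= 2) for Binomial(12, 0.39) = 9.5%.

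**4. Possible size.** Let s be the share of true CLL responders who cannot be scored. The documents give no value, so s is an assumption. Recorded ORR = true ORR x (1 - s); for example, 0.39 x 0.80 = 0.312.

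| s | Recorded ORR, true 39% | P(2 or fewer of 12) | Recorded ORR, true 50% | P(2 or fewer of 12) |
|---|---|---|---|---|
| 0 | 39.0% | 9.5% | 50.0% | 1.9% |
| 10% | 35.1% | 15.0% | 45.0% | 4.2% |
| 20% | 31.2% | 22.5% | 40.0% | 8.3% |
| 30% | 27.3% | 32.3% | 35.0% | 15.1% |

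For the final ORR, s should count only responders who are never recorded as CR later. At the interim, after the first response assessment, a late CR cannot help anyone still on treatment.

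**5. At the planned 30 subjects**, each lost responder costs 1/30 = 3.3 points: 15/30 = 50% (exact 95% interval 31.3 to 68.7), 13/30 = 43.3% (25.5 to 62.6), 11/30 = 36.7% (19.9 to 56.1). In a smaller cohort each costs more.

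**The case against.** Several points on the other side stand.

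- The node row speaks of the enlarged node(s), so an investigator may fairly treat it as not applicable when there are none. That makes the node line ambiguous rather than a clear bar. It does nothing for the lymphocyte line.
- Section 12.7 is based on a 2008 guideline that cannot be consulted here, and inclusion 10 requires a diagnosis under the same guideline. Either could narrow the affected group. Neither removes the PR/CR anomaly within the table.
- A normal lymphocyte count can still halve, so not every subject in the group is lost.
- CR timing is not uniform across the protocol. Table 14 lists CLL marrow to confirm CR without the 2-month delay, and the flow chart places as-needed marrow in the on-treatment column.
- The CLL cohort closed on 30-APR-2019 and all its subjects are off treatment. CLL ORR is a descriptive secondary result with no hypothesis test (Sections 3.2 and 8.3).
- Changing a response rule after an open-label cohort has closed carries its own risk, which is why both results should be shown.

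A reader might infer that CLL subjects in remission on treatment score SD in general. They do not: those with enlarged nodes and clearly raised lymphocytes can score PR on treatment. A reader might also infer that the interim rule wrongly closed the cohort. The documents do not support that either: closure was for lack of accrual, 39% is the upper bound that 2/12 excludes, and 2 or fewer responses prompt a review of all safety and efficacy data rather than an automatic stop.

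**Conclusion.** The gap is real but confined to part of one cohort. Under the literal text, CLL subjects entering with normal or near-normal lymphocytes, or on one reading without enlarged nodes, can be scored SD while responding on treatment. Those in the last row of the second table under step 2 can never be scored as responders.

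The direction is settled, since the rule can only remove responders. The size is not. It rests on an unstated share that may be zero, so a reader should not take it as shown that the CLL ORR is biased. The drop from 39% to 31% assumes that 20% of responders are affected and that none of them is recorded as CR later. The interim probabilities are chances of meeting the review trigger, not of closing the cohort in error. The consequence that remains is for the reported CLL ORR and duration of response.

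**What to change.** Before database lock, in the supplemental SAP that Section 8.0 provides for:

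1. Apply the liver/spleen qualifier to the PR lymphocyte and node lines. Values normal at baseline must stay normal, and at least one abnormal parameter must improve by 50%. Limits already in the protocol can define abnormal: nodes of 1.5 cm or more (Section 7.1.2.8.1) and lymphocytes at or above the CR limit of 4 x10^9/L. With that limit, entry counts from 4 to below 8 still face a PR test stricter than CR, so state how they are scored.
2. Report how many CLL subjects entered with normal nodes, or with lymphocytes below 4 or from 4 to below 8, and how many change category.
3. Give CLL ORR under the literal and the qualified rule, labelling the second as added after the cohort closed.
4. Reconcile the CR timing in Section 12.7 with Table 14 and the flow chart. Do not re-derive CR from CT and blood counts alone, because CR also needs marrow.

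No new visits or tests are needed. The cost is a small extra derivation from data already collected and a second ORR figure specified late in an open-label cohort.

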7.1.2.8 Assessment of Disease and Tumor Response

7.1.2.8.1 CLL Response Assessments

Disease assessments or scans performed as part of routine clinical management are acceptable for use as the screening scan if they are of diagnostic quality and performed within 28 days prior to Cycle 1 Day 1.

CT scans of the neck, chest, abdomen, and pelvis will be obtained at screening within 28 days of Cycle 1 Day 1. Follow-up CT scans of the neck should be performed if enlarged lymph nodes (defined as ≥ 1.5 cm) are detected on the screening CT neck scan or if medically indicated by the discretion of the treating physician.

CT scans will be repeated every 3 cycles (approximately 9 weeks) despite any delays in treatment. CT scans will be read locally.

Response will be determined locally according to the iwCLL criteria, using results of the subject's CT scan, hematology laboratory results (complete blood counts), and presence of CLL symptoms as described in Section 12.7. Response assessments should be completed in conjunction with the subject's CT scan schedule.

If medically appropriate, a confirmatory assessment of the initial progression event should be performed within 9 weeks. A CT scan of the neck (if indicated), chest, abdomen and pelvis and hematology laboratory (complete blood counts) will be obtained, and the presence of CLL symptoms will be determined at each response assessment time point.

7.1.2.8.2 Multiple Myeloma Response Assessments:

7.1.2.8.2.1 Myeloma Laboratory Testing Disease Measurements

Baseline

For subjects with MM, collect serum and urine samples within 28 days of Cycle 1 Day 1 for baseline disease assessment. Baseline serum and urine (24 hr) M protein levels will be assessed by electrophoresis and immunofixation. Free light chain (FLC) levels and ratio will also be assessed.

Serum electrophoresis (SPEP)

If serum M protein by electrophoresis (SPEP) ≥ 1 g/dL at baseline, SPEP will be assessed after each cycle.

Urine electrophoresis (UPEP)

If urine M protein (24 hr) by electrophoresis (UPEP) ≥ 200 mg, UPEP (24 hr) will be assessed after each cycle.

FLC

For subjects with non-secretory myeloma (SPEP < 1 g/dL and UPEP < 200 mg/24 hr) at baseline, but serum light chain ≥ 10 mg/dl, serum FLC will be assessed after each cycle.

Best Response

Laboratory assessments should be repeated to confirm best response, including SPEP and UPEP, serum and urine immunofixation, and FLC. Bone marrow biopsy is recommended to confirm CR.

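### The hemoglobin limit in the CLL cytopenia progression criterion is printed with its sign the wrong way round; the effect is confined to PFS and DOR in the closed CLL cohort

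*Combined protocol and SAP*

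**What the plan says.** Section 12.7 sets out the CLL response table. It presents the 2008 iwCLL guideline "with the following clarifications/revisions".

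- **Progressive disease, general rule:** "Characterized by at least one of the following during or after therapy". One item is enough.
- **Cytopenia item, lead-in:** "Progression of cytopenia attributable to CLL which occurs at least 3 months" after treatment, documented by the two lines that follow.
- **Hemoglobin line:** "decrease of Hb levels by >20 g/L or to >100 g/L".
- **Platelet line, directly below:** "decrease of platelets by $>50\%$ or to $<100 \times 10^9$/L if the marrow biopsy demonstrates an infiltrate of clonal CLL cells".
- **Hemoglobin for CR (in g/dL):** ">11 without red blood cell transfusion or need for exogenous erythropoietin".
- **Hemoglobin for PR:** ">11 g/dL (110 g/L), or 50% improvement over baseline", again without transfusion or erythropoietin.

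Elsewhere, CLL inclusion criterion 12 (Section 5.1.2) gives hemoglobin under 11 g/dL as anemia. Section 7.1.2.8.1 states "Response will be determined locally according to the iwCLL criteria" and points to Section 12.7 for the description. Section 8.4.1 bases the efficacy endpoints on investigator assessment under Section 7.1.2.8, and defines PFS and DOR by the first documented progression or death. No other section gives a different hemoglobin limit for progression.

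**The concern.** A limit reached by a decrease should be a ceiling that the value falls below. Here it is a floor that the value stays above. Because Section 12.7 announces that it revises the published guideline, a site could take the printed sign as intended.

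At stake are the progression dates that feed the CLL PFS and DOR estimates. A limit with the wrong sign can fail to register a CLL-related decline in hemoglobin, and can allow a small change at a higher level to satisfy the item. Assessment is local. Section 7.1.2.7.1 says only that the sponsor may request images or laboratory results for independent review, so no planned central reading would pick up a misapplied limit.

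**Working it through.** No sample size, power or precision figure depends on this line, so there is no stated figure to reproduce. The check is one of logic.

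**Inputs.** Hemoglobin limits of 20 g/L and 100 g/L, and the platelet limit with its downward sign (Section 12.7, progressive disease). CR and PR hemoglobin level: 11 g/dL × 10 = 110 g/L (Section 12.7). Anemia: under 11 g/dL, that is under 110 g/L (Section 5.1.2, criterion 12).

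**Rules.** Let b be the hemoglobin from which the fall is measured and v the later value, with b > v, both in g/L.

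- As printed: (b − v) > 20, or v > 100.
- With the second sign reversed, as in the platelet line: (b − v) > 20, or v < 100.

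The lead-in conditions are the same under both, so they are set aside first and restored below.

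| b to v | Fall | Item as printed | Sign reversed |
|---|---|---|---|
| 130 to 125 | 5 | met | not met |
| 120 to 115 | 5 | met | not met |
| 111 to 101 | 10 | met | not met |
| 120 to 100 | 20 | not met | not met |
| 115 to 96 | 19 | not met | met |
| 110 to 95 | 15 | not met | met |
| 105 to 90 | 15 | not met | met |
| 95 to 80 | 15 | not met | met |
| 130 to 105 | 25 | met | met |
| 130 to 95 | 35 | met | met |

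In general, the two rules agree for every fall of more than 20 g/L. For falls of 20 g/L or less they give opposite answers at every later value except exactly 100 g/L.

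**Restoring the lead-in.** The item needs progression of a cytopenia, attributable to CLL, at least 3 months after treatment.

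- *Missed progression.* The lead-in does not help here. A CLL-related fall from 110 to 95 g/L satisfies the lead-in but is not documented by the hemoglobin line as printed.
- *Over-calling.* The lead-in narrows this side. Falls of 130 to 125 and 120 to 115 end above 110 g/L, a level that the protocol's own figures do not class as anemia. A fall from 111 to 101 ends below 110 g/L; if the investigator attributes it to CLL, the item is met as printed. Section 12.7 does not define cytopenia. If the 110 g/L figure is taken as its boundary (an assumption), the exposed range is later values above 100 and below 110 g/L, reached by a fall of 20 g/L or less.

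**The case against.** The strongest reply is that the hemoglobin line does not stand alone. A reader might infer that any drop that stays above 100 g/L, even 130 to 125 in a subject in CR, is progression as written. The documents do not support that: the lead-in requires a cytopenia that is progressing and is attributable to CLL, and the marrow clause at the end of the platelet line may be meant to govern both lines. This stands, and it limits the over-calling side.

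A reader might also infer that cytopenic progression in general goes unrecorded. It does not. Any CLL-attributable fall of more than 20 g/L still counts, as do the platelet, node, liver or spleen and lymphocyte items. The flow chart continues CT, response assessment and constitutional symptoms at the efficacy follow-up visits, and Section 7.1.2.8.1 asks for a confirmatory assessment of a first progression where medically appropriate. This stands too: only the smaller falls that end below 100 g/L are lost, and only if nothing else triggers.

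Third, Section 7.1.2.7 and Table 19 cite the iwCLL guideline directly, so sites and analysts had that source and may never have used the printed sign. That is possible, but Section 7.1.2.8.1 sends them to Section 12.7, whose table claims to revise the guideline. The documents do not say which was followed.

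Finally, the defect is a single character in text read from a PDF by a program. The platelet sign beside it was read in the expected direction, which makes a reading error less likely but does not exclude it.

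**Conclusion.** The concern holds in a limited form. The printed hemoglobin limit contradicts the platelet line, the CR and PR levels and the anemia figure in the inclusion criteria. It is most likely a typographical inversion, and it sits in the working rule for CLL progression.

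The reach is small. PFS and DOR are secondary endpoints, summarized by Kaplan-Meier methods with no formal hypotheses (Section 8.3, Table 19). ORR, DLT, the sample size and the futility rule do not use this line. The CLL cohort closed to enrollment on 30-APR-2019, its subjects are off treatment, and those remaining are in survival follow-up, which is by telephone (Sections 1.0 and 7.1.5.4.2). Correcting the sign should therefore change no future CLL assessment; what remains is a retrospective check. The documents do not show that any subject was misclassified.

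The internal evidence settles the direction of the limit, not its value. A reader might infer that the CR definition confirms a limit of 100 g/L, but CR and PR use 110 g/L. The conclusion assumes that the issued page carries the same sign as the text read here.

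**What to change.** 1. Check the sign on the protocol page as issued.
2. Reconcile the hemoglobin limit in Section 12.7 with the platelet line, the CR and PR levels and the cited iwCLL guideline. State whether the marrow clause applies to both lines.
3. Record in the supplemental SAP which limit was applied to CLL progression. Section 8.0 already provides for changes documented there before final database lock and referenced in the study report.
4. Before the CLL PFS and DOR analyses, list (a) every progression call that rests on hemoglobin alone and (b) every off-treatment fall to below 100 g/L that was not called progression. If either list has entries, report how the estimates change when those calls are re-read under the reconciled limit.

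The cost is one character, a short supplemental SAP entry and one listing in a closed cohort. List (b) needs off-treatment hemoglobin values: Section 7.1.2.8.1 asks for blood counts at each response assessment, but the flow chart does not appear to mark one at the efficacy follow-up visits. The listing should therefore say which subjects have no such value.
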